7.0 Risks

7.1 The following risks associated with participation are considered:

7.1.1 Hypoglycemia

Hypoglycemia is encountered intermittently by all patients with T1DM as part of the natural consequence of diabetes management with exogenous insulin administration, and we do not anticipate that this risk will be increased by utilizing enzyme replacement treatment.

We will use the following safety provisions to minimize risk of hypoglycemia: participants will monitor their blood sugar via continuous glucose monitor. Participants will be reminded that if hypoglycemia occurs, the patient should treat hypoglycemia with oral intake (administer 15 grams of carbohydrates in liquid form or with glucose tablets) if the patient is responsive and able to consume the treatment orally. If the patient is unresponsive, the study team would instruct the participant's caretaker to administer intramuscular glucagon. The study team will ensure that the participants have an up-to-date glucagon kit at time of enrollment.

7.2 Discussion of Risks as Part of the Consent Process

The study team will discuss all procedures, risks, and benefits with potential study participants, as part of the consent process. An IRB approved written informed consent document will be required for participation in this study. It is understood that consent is a process and not a discrete event. A participant's decision to withdraw consent will be respected throughout the duration of each subject's participation in this study. It is also understood that there may be asyet unknown or unanticipated adverse effects of this study. The study team will continually monitor for these effects and consider altering the protocol as needed to ensure patient safety. Changes in the procedures of the study, as well as any change(s) in the risks and/or benefits will be presented to and discussed with the subjects upon approval from the IRB for implementation of such revision(s), and any IRB revised written consent will be signed, as appropriate.

8.0 Reporting of Adverse Events or Unanticipated Problems involving Risk to Participants or Others

- 8.1 Serious Adverse Events
 - 8.1.1 Defining Serious Adverse Events Consistent with FDA guidelines, serious adverse events (SAEs) will be defined as any untoward medical occurrence that:
 - requires inpatient hospitalization
 - results in persistent or significant disability
 - is suspected to cause a congenital anomaly or birth defect in a subject's unborn child
 - is life-threatening
 - results in death
 - is considered to be an important medical event based on appropriate medical judgement (e.g. bronchospasms requiring emergency department referral, seizures that might not result in hospitalization).
- 8.2 Assessing relationship between a SAE and relationship to study procedures An SAE's relationship to the study procedures will be assessed and graded as either: not related, unlikely, possible, probable, or definite.

8.3 Assessing whether an AE is an anticipated problem

Any AE will be assessed for whether or not it was an anticipated problem. In accordance with Department of Health and Human Services guidance and consistent with 45 CFR part 46, an "unanticipated problem" will include any incident, experience, or outcome that meets all of the following criteria:

- 1. unexpected (in terms of nature, severity, or frequency) given
 - a. the research procedures that are described in the protocol-related documents, including the IRB-approved research protocol and informed consent document; and
 - b. the characteristics of the subject population being studied; related or possibly related to participation in the research; and
- 2. suggests that the research places subjects or others at a greater risk of harm.
- 3. related or possibly related to participation in the research;
- 4. suggests that the research places subjects or others at a greater risk of harm than was previously known or recognized.

8.4 Hypoglycemia

Hypoglycemia Instances of significant impairment consistent with hypoglycemia and requiring assistance (ie, often referred to as "severe" hypoglycemia), even in the absence of a blood glucose reading, are classified as "Level 3 Hypoglycemia" (IHSG 2017). Level 3 hypoglycemia may include cognitive impartment, altered/loss of consciousness, confusion, seizure, syncope/fainting, or coma, and support may be general assistance, glucagon, or oral carbohydrate (ie, fruit juice or glucose tablets). Such episodes may or may not require medical attention or hospitalization. This study will consider clinically significant hypoglycemia to be Grade 3 or greater hypoglycemia as defined below. Grade 1 and Grade 2 hypoglycemia are expected normal consequences of T1D and will not be recorded as AEs for this protocol. For AE reporting purposes, the severity of a hypoglycemia event should be identified by the Investigator and classified according to CTCAE v5.0 as follows:

- Grade 3 hypoglycemia: 30-39 mg/dL (1.7–2.1 mmol/L). This is considered severe or medically significant but not immediately life-threatening. Hospitalization or prolongation of hospitalization may be indicated. It is likely to be disabling and to limit self-care.
- Grade 4 hypoglycemia: ≤29 mg/dL (1.6 mmol/L). This is considered life threatening (eg, seizures) with urgent intervention indicated.
- Grade 5 hypoglycemia: Hypoglycemia resulting in death.

8.5 Unanticipated, non-serious AEs

All unanticipated, non-serious AEs and the study team's response to the non-serious AE will be included in a report at the time of annual continuing review. The PI will review the AEs and notify the IRB of any changes needed to the protocol. If needed, appropriate changes will be made to the consent form.

8.6 Unanticipated SAEs

In accordance with IRB policy, any unanticipated SAE that is considered possibly related to participation in the study will be reported within 7 calendar days of the PI's notification of the event to the IRB. The study team will continue to follow or obtain documentation of the resolution of any SAE.

8.7 Adverse Event Reporting

The annual summary of all unanticipated adverse events and any audit reports will be sent to the IRB at the time of continuing review.

This protocol will be reviewed annually (at a minimum) by the Vanderbilt IRB. The goal of this process is to determine the risks and benefits of the study in the actual experience of subjects and that measures taken to minimize risks are adequate

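### Section 8.4 defines severe hypoglycaemia by need for assistance but records AEs by glucose grade, so an assisted non-fatal event at 40 mg/dL or above is left out unless it is an SAE

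*Protocol*

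**What the plan says.** Protocol section 8.4 (Hypoglycemia) uses two classifications.

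- **Level 3, by function.** Impairment consistent with hypoglycaemia that requires assistance is severe. Such instances, "even in the absence of a blood glucose reading, are classified as" Level 3. The examples run from confusion to seizure and coma, and the help given may be as little as juice. The section adds: "Such episodes may or may not require medical attention or hospitalization".
- **CTCAE v5.0 grade, mainly by glucose.** The section then sets the study's threshold on this second scale: "This study will consider clinically significant hypoglycemia to be Grade 3 or greater hypoglycemia as defined below". The lower grades are excluded from the AE record: "Grade 1 and Grade 2 hypoglycemia are expected normal consequences of T1D and will not be recorded as AEs for this protocol". The listed grades begin with "Grade 3 hypoglycemia: 30-39 mg/dL", followed by Grade 4 at 29 mg/dL or below and Grade 5, death. Grades 1 and 2 are not defined.

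Once introduced, Level 3 is not used again: no grade, AE trigger or reporting step refers to it. The SAP has no rule for recording hypoglycaemia as an AE.

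**The concern.** The definition of a severe event and the rule for what is recorded do not meet. An episode can be severe because the participant needed help, and still fall outside the AE record because the glucose value was not low enough.

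Hypoglycaemia is the only specific risk listed in section 7.1, and 7.1.1 says of it that "we do not anticipate that this risk will be increased by utilizing enzyme replacement treatment". Checking that expectation depends largely on the AE record. Section 8.3 states: "Any AE will be assessed for whether or not it was an anticipated problem". Its criteria include unexpected severity and frequency. An assisted episode that never becomes an AE may not reach that assessment, and frequency cannot be judged from events that were not counted.

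The CGM download listed in 6.1.4.2 does not fill the gap. It would hold the glucose trace but not whether anyone had to help.

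**Working it through.** The documents state no figure to reproduce. The check applies the 8.4 rule to an assisted, non-fatal event at different glucose values.

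**Inputs**
- Level 3: assistance needed, no glucose limit (8.4).
- Grade 3: 30-39 mg/dL; Grade 4: 29 mg/dL or below; Grades 1-2 not recorded (8.4).
- SAE criteria: hospitalisation, disability, life-threatening event, death, birth defect, important medical event by judgement (8.1.1).
- CGM categories collected: below 70 and below 50 mg/dL (6.1.4.2).
- 15 participants (10.1) and four 7-day blocks, two of them on treatment (2.0, Aim 1).

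**Rule applied to an assisted, non-fatal event that is not an SAE**

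| Glucose (mg/dL) | Level 3? | Grade from the listed bands | Recorded as AE? |
|---|---|---|---|
| 25, 29 | Yes | 4 | Yes |
| 30, 39 | Yes | 3 | Yes |
| 40, 45, 50, 54, 60, 69 | Yes | Below 3 | No |
| No reading | Yes | None can be assigned | Undefined |

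**Width of the gap.** The highest glucose in a recorded non-fatal grade is 39 mg/dL, so the gap starts at 40. If the below-70 CGM category marks the upper end of low glucose, the gap is 40-69 mg/dL. The 40-49 part lies inside the lowest CGM category the protocol collects (below 50), yet outside the recorded grades.

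**SAE route.** Section 8.1.1 would catch an assisted event that led to hospitalisation or was life-threatening. It also catches one that "is considered to be an important medical event based on appropriate medical judgement", with seizures given as an example. It does not clearly catch confusion put right with juice given by someone else, although that fits Level 3.

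**Planned exposure**
- All blocks: 15 × 4 × 7 = 420 participant-days; 420 / 365.25 = 1.15 participant-years.
- On Creon or placebo: 15 × 2 × 7 = 210 participant-days.

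These totals assume that all 15 participants complete all four blocks. The documents give no rate of assisted hypoglycaemia, so no expected count is calculated.

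**The case against.** The strongest reply is that 8.4 can be read as a whole. It calls assisted episodes severe, leaves the investigator to identify severity, and describes Grade 3 in terms of severity, disability and limited self-care. An investigator might therefore grade an assisted episode as Grade 3 whatever the glucose. That reading would also give the Level 3 sentences a purpose. However, the descriptors follow each glucose band as a comment on it, and grading is to be done by the list as given. They are not offered as a second way to qualify. If the sponsor intends that reading, the section needs to say so, or two investigators may record the same event differently.

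Other points stand in part:

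- **The boundaries are inferred.** The 40 mg/dL limit follows from the top of Grade 3. The 69 mg/dL limit borrows a CGM cut-off that has no stated role in AE grading.
- **There are other safety nets.** Section 8.3 defines an unanticipated problem as an incident, experience or outcome, which is wider than a recorded AE, and 7.2 promises continuing monitoring for unexpected effects. Neither provision requires an assisted event to be written down.
- **The gravest cases are largely covered.** Seizure is named in 8.1.1, and coma or loss of consciousness could readily qualify as an SAE. The remainder is mainly milder assisted episodes.
- **Downstream effect is limited.** Sections 8.5 and 8.7 send only unanticipated AEs to the annual review, and hypoglycaemia is an anticipated risk. A single extra entry might not be reported, although an unexpected severity or frequency would be.

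**Conclusion.** The concern holds. Followed as written, section 8.4 leaves a non-fatal assisted event at 40 mg/dL or above out of the AE record unless it meets the SAE definition. It does not settle what happens to an assisted event with no reading. This is a conflict between a stated definition and a stated rule, not merely missing detail.

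The conclusion rests on two assumptions: that unlisted values above 39 mg/dL belong to Grades 1-2, and that the Grade 3-4 descriptions do not act as independent criteria.

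Its practical size is modest. Over at most 1.15 participant-years the number of missed events may be small or zero. No planned efficacy analysis and no planned between-treatment comparison of AEs changes. The cost is an incomplete safety record for the trial's one specifically listed risk, in a pilot meant to inform a larger study. It should be corrected.

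**What to change.** Reconcile the two definitions in 8.4 for recording purposes. One sentence is enough: a hypoglycaemic event is recorded as an AE if it meets either Level 3 (assistance needed, with or without a reading) or Grade 3 and above. Record the glucose value where available and the study period in which the event occurred (run-in, week A, washout or week B).

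This concerns only what is written down; how episodes are managed is untouched. The cost is that sentence, one AE form field and possibly a few more AE entries.

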9.0 Study Withdrawal/Discontinuation

Subjects will be free to withdraw from the study at any time, which will be made clear at enrollment. Subjects will be withdrawn from the study if:

- Pregnancy is detected

- The PI's (or designated MD, NP, or PA KSP) medical judgement is that participation places the subject at risk for harm.

10.0 Statistical Considerations

10.1 Recruitment

We have targeted an accrual of 15 participants in this pilot study. We will estimate the effect size and variance of the intervention on glycemic variability and symptoms. We will also ascertain the intra-individual variation from comparison between our two non-treatment intervals (run-in and wash-out periods) which will set a lower bound on measurable effects. To estimate the pilot study's optimum accrual, we utilized the method of Whitehead et al. which proposes stepped increases in sample size based on the anticipated standard difference, d, between interventions^{1,2}. We defined the minimum important difference (MID) in low blood glucose index, a measure of low blood glucose from CGM data) between enzyme replacement and placebo interventions as 1 (difference in values of 3 for more variable and 2 for less variable as reflected in clinical experience) and estimated a pooled SD of 1.29 based on our review of CGM data from other studies. If d=MID/SDpooled=1/1.29=0.77, a sample size of 15 participants per arm will optimize future sample size calculations for a definitive study.

10.2 Statistical Analysis Statistical analysis will be performed using a paired samples t-test to compare differences between the two groups.

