2.0 Rationale and Specific Aims

We hypothesize that patients with T1DM who have reduced pancreatic volume will have improved glycemic responsiveness, reduced hypoglycemia, and improved symptoms of pancreatic exocrine insufficiency (PEI) when treated with pancreatic enzyme replacement. To test our hypotheses, we will employ a double-blinded crossover study. This study will be a pilot study to gather preliminary information on potential effect size in preparation for a larger study if supported by these results. The study will enroll approximately 15 adult subjects with T1D who will receive both pancreatic enzyme replacement (Creon) or placebo each for 7 days in a random order. The effect of the intervention will be monitored by continuous glucose monitoring, diet recording, capsule counts, a mixed-meal tolerance test, and a survey to assess symptoms of PEI. This study design will allow for estimation of the effect of pancreatic enzyme replacement on the measured parameters.

Aim 1 will provide preliminary estimates of the effect of enzyme replacement on glucose responsiveness, variability, and hypoglycemia. We will download and analyze CGM data to determine changes occurring in measures of glycemic variability and in the duration and severity of hypoglycemia. Data will be divided into 4 7-day blocks including a run-in period, treatment A, a wash out period, and treatment B. Participants will track their meal composition, report daily exercise duration, and a capsule count will be obtained. At the end of treatment A and treatment B, participants will undergo a mixed meal tolerance test (MMTT) in which glucose, C-peptide, GLP-1, GIP, and glucagon will be measured at defined timepoints.

Aim 2 will provide an initial assessment of the effect of enzyme replacement on symptoms of pancreatic exocrine insufficiency in T1D. We will use the PEI-Q to quantitate symptoms of PEI and their relative change during enzyme replacement at each of the 4 intervals. The frequency and degree of PEI symptoms has not been objectively measured in T1D patients previously.

We will obtain information on the adherence to the intervention and will obtain initial information on median and standard deviation for measured variables that will inform future studies. We will perform a paired t-test to provide an initial assessment of outcomes between groups.

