6.1.1.6 Randomization and Treatment Plan

Participants will be randomized for order in which enzyme replacement or placebo is received. An equal number of participants will receive either order (A/B or B/A). Participants will receive a range of 50,000-100,000 lipase units per meal (approx. 2 Creon 36,000 capsules) and 25,000-50,000 per snack (1 capsule). The participant will be instructed to take same number of capsules of placebo. Participant and provider will be blinded to capsule assignment.

- 6.1.2 Study visit (baseline)
 - 6.1.2.1 Demographic and history information will be obtained.
 - 6.1.2.2 Participant will be counseled on using and uploading devices and information.
 - 6.1.2.3 Participant will complete a baseline Mixed Meal Tolerance Test (MMTT). The test will be administered according to the well established practices used in the TrialNet clinical T1D research program and described in the included appendix. This baseline visit will take place in the Adult Clinical Research Center (CRC).
- 6.1.3 Study Visit (end of week A)
 - 6.1.3.1 On last day of week A, subject will have an MMTT at the Adult CRC.

6.1.4 Study Visit (end of week B/end of study) This visit will include an MMTT at the Adult CRC and will be scheduled on the last day of week B.

6.1.4.1 History and measurements

Protocol Version #: 6 Protocol Date: 04DEC2023 The PI or designee will review each subject's clinical history and take anthropometric measurements.

6.1.4.2 Continuous glucose monitor and insulin pump data collection

Continuous glucose monitor and insulin pump will be downloaded into a HIPAA and FDAcompliant cloud-based, data-integration platform such as Dexcom Clarity, Medtronic Carelink, or Tidepool.

Information that will be collected from the continuous glucose monitor download will include (but not be limited to):

- Percent of time spent above the glycemic target of 140 mg/dL
- Percent of time spent in the glycemic target of 70 140 mg/dL
- Percent of time spent below the glycemic target of 70 mg/dL
- Percent of time spent in hypoglycemia below 50 mg/dL
- Average blood glucose
- Blood glucose standard variation
- All blood glucose values during the study interval

Information that will be collected from the insulin pump download will include (but not be limited to):

- Average total daily dose of insulin
- Average bolus amount of insulin per day
- Average basal amount of insulin per day

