Pancreatic enzyme replacement and glucose regulation in Type 1 diabetes

NCT05266963

Statistical Analysis Plan

12/4/2023

Statistical Analysis Plan

NCT05266963 - Pancreatic Enzyme Replacement and Glucose Regulation in Type 1 Diabetes (CREON)

Background

In T1D, there is significant reduction in pancreas volume. The biological impact of this is not known. Because islet cells make up a small fraction of pancreas size, the major reduction in volume is due to loss of exocrine tissue. Since patient with T1D have substantial loss of exocrine tissue and pancreatic enzymes support glucoe regulation and pancreas function, this study tests the hypothesis that pancreatic enzyme replacement will improve C-peptide secretion to regulate glucose excursions and/or will improve symptoms of pancreatic enzorine insufficiency. This document provides additional description of the analysis plan and complements the protocol document where study details are provided.

Primary objective

Aim 1: To assess impact of pancreas enzyme replacement on C-peptide auc in subjects with T1D and reduced pancreas volume

Aim 2: To assess the impact of pancreas enzyme replacement on symptoms of pancreatic exocrine insufficiency (PEI) in T1D.

Secondary Objectives

Secondary assessments will be made to explore mechanisms of effect if the primary outcome is met. These could include analysis of CGM data, measure of circulating hormones and cytokines, assessment of dietary intake.

Trial Design

The study is a single center, double-blinded randomized cross over design in which subjects receive Creon or placebo each for 1 week with a 1 week washout period between.

Eligibility

Inclusion Criteria	Exclusion Criteria
 Diagnosed with T1DM for at least	 History of celiac disease or
12 months Age over 18 Total daily dose of insulin greater	inflammatory bowel disease Unwilling to temporarily discontinue
than 0.6u/kg/day	use of medication or supplements

 Current use of a CGM 	other than insulin to control blood
 Current use of smart phone 	glucose
 Able to read and speak English 	 Pregnant or breast feeding
 Willingness and ability to download and provide CGM and pump (if applicable) data Reduction of pancreas volume (<0.6mL/kg BW) 	 Following a restrictive diet (such as very low carb diet) History of major bowel or bariatric surgery

Treatment

Participants will continue their standard care for diabetes with calculation and adjustment of doses per their primary endocrinologists.

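### The run-in versus wash-out comparison is pooled over both treatment orders, so the planned within-person lower bound may mix any after-effect of Creon with week-to-week noise (minor)

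*Protocol*

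**What the plan says.** Protocol section 10.1 names a pilot output beside the effect size and variance: the "intra-individual variation from comparison between our two non-treatment intervals (run-in and wash-out periods) which will set a lower bound on measurable effects". Both weeks are called non-treatment intervals and are compared in all participants together.

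The wash-out follows the first treatment week. Protocol section 2.0: "Data will be divided into 4 7-day blocks including a run-in period, treatment A, a wash out period, and treatment B". The SAP (Trial Design) gives the same layout: "subjects receive Creon or placebo each for 1 week with a 1 week washout period between".

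On order, Protocol section 6.1.1.6 says: "An equal number of participants will receive either order (A/B or B/A"). On numbers, section 10.1 says: "We have targeted an accrual of 15 participants in this pilot study". Fifteen cannot be halved, so the split is 7 and 8.

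On background care, the SAP (Treatment) says: "Participants will continue their standard care for diabetes with calculation and adjustment of doses per their primary endocrinologists".

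Neither document splits the run-in versus wash-out comparison by order, sets aside the first wash-out days, checks for persistence or gives a reason for one week. The SAP does not mention the comparison.

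**The concern.** The run-in comes before any study capsule. The wash-out comes after placebo in one order and after Creon in the other. The two weeks are equivalent in everyone only if nothing persists once Creon stops, and the plan neither states nor examines that assumption.

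The documents contain one conceivable route for persistence. Insulin doses continue to be adjusted under standard care, and a dose changed in response to a Creon week could stay changed in the next week. If that happened in the Creon-first order only, the pooled difference would have a shifted mean and a larger spread, and neither could be told apart from ordinary variation.

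At stake is one descriptive output of a pilot whose purpose is to prepare a larger study. An inflated value would overstate how large an effect must be before it is measurable. Pooling also leaves unused the only direct information that the design yields on the week after Creon stops.

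**Working it through.** **The plan's own figure.** Section 10.1 gives no value for the lower bound, so there is none to reproduce. Its other figure is d = 1/1.29 = 0.775, printed as 0.77. The step from d to 15 per arm rests on a cited source and cannot be checked here. It does not affect this point.

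**Inputs from the documents**
- Minimum important difference in LBGI "between enzyme replacement and placebo interventions as 1 (difference in values of 3 for more variable and 2 for less variable" (section 10.1).
- SD: the authors "estimated a pooled SD of 1.29 based on our review of CGM data from other studies" (section 10.1). It is not stated to be a within-person or a weekly SD.
- Share who took Creon first: f = 7/15 = 0.467 or 8/15 = 0.533.

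**Assumptions (not in the documents)**
- rho, the correlation between a person's run-in and wash-out values: 0.3 to 0.9.
- c, the mean after-effect over the 7-day wash-out block in those who took Creon first. An effect of 1 that fades linearly over k days averages k/(2 × 7): 0.07 for one day, 0.14 for two, 0.5 for seven. An effect of 1 lasting all week gives c = 1.

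**Formulas.** Let D = wash-out minus run-in.
- Without after-effects: Var(D) = 2 × 1.29² × (1 − rho).
- Pooled over both orders with an after-effect: Var(D) = 2 × 1.29² × (1 − rho) + f(1 − f)c², where f(1 − f) = 56/225 = 0.249 for either split.
- Shift in the mean of D: f × c, that is 0.47c to 0.53c.

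**Example, rho = 0.5.** The clean SD is √(2 × 1.6641 × 0.5) = 1.290. With c = 1 the SD is √(1.6641 + 0.249) = 1.383, or +7.2%. With c = 0.5 it is √(1.6641 + 0.062) = 1.314, or +1.9%.

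| rho | Clean SD of D | c = 0.07 to 0.14 | c = 0.5 | c = 1 |
|---|---|---|---|---|
| 0.3 | 1.526 | under 1% | +1.3% | +5.2% |
| 0.5 | 1.290 | under 1% | +1.9% | +7.2% |
| 0.7 | 0.999 | under 1% | +3.1% | +11.8% |
| 0.9 | 0.577 | under 1% | +8.9% | +32.2% |

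The protocol gives no formula for the bound. If it is a root mean square of D, the mean shift enters too and f(1 − f)c² becomes f × c². For c = 1 the inflation is then about 10% (rho 0.3) to 61% (rho 0.9, f = 8/15).

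**Set against sampling error.** The 95% confidence interval for an SD from 15 people runs from 0.73 to 1.58 times the estimate. Every SD inflation in the table is smaller than that upper margin.

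**What a split by order could show.** The 95% half-width for the difference in mean D between 7 and 8 participants is t(13 df) × SD × √(1/7 + 1/8) = 2.160 × 0.518 × SD = 1.118 × SD. At rho 0.5, 0.7 and 0.8 (SD 1.290, 0.999, 0.816) this is 1.44, 1.12 and 0.91 LBGI. Power to detect c = 1 at the two-sided 5% level is 28%, 43% and 59%.

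**The case against.** The strongest reply is that nothing in the documents says Creon has any after-effect on glucose or symptoms, or how long one would last. If c = 0 there is no bias. A reader might infer from the layout that the bound does contain after-effects; the documents support only that it may. The insulin route is likewise conjecture: the SAP says that doses continue to be adjusted under standard care, not that a blinded week would prompt a change or that a change would last. This stands.

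A reader might also infer that an inflated bound could lead to a real Creon effect being declared unmeasurable. The documents contain no such rule. The protocol's paired t-test and the SAP's Wilcoxon and t-tests do not use the bound, nor does the target of 15. The protocol does not say how the bound would be applied in a later study, and an inflated bound errs on the cautious side. This stands too.

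The output is also peripheral. The SAP's primary outcomes are C-peptide AUC and the PEI-Q severity score. The study visits schedule no mixed-meal test in the wash-out, and section 6.1.4.4 schedules no PEI-Q there, although Aim 2 in section 2.0 refers to all four intervals; those passages must be reconciled. In practice the bound concerns CGM and diary data.

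Finally, it is tempting to think that a split by order would settle whether 7 days is enough. It would not. With 7 against 8 people, a null result leaves room for an after-effect of about the minimum important difference.

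What survives is narrow: the pooled estimate relies on an unstated assumption that the randomised order makes almost free to drop.

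**Conclusion.** Minor. Section 10.1 treats the two weeks as equivalent although about half of the participants have just stopped Creon, so the pooled figure may mix after-effects with noise. Whether it does is unknown.

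The plausible cost is small: under 1% on the SD if an effect of 1 fades in one to two days, about 1% to 9% for a mean after-effect of 0.5, and about 5% to 32% only if an effect as large as the full minimum important difference lasts all seven days. The mean shifts by about half of the after-effect. These figures assume that 1.29 applies to weekly LBGI, that the correlation lies between 0.3 and 0.9, and that the after-effect is the same in everyone who took Creon first. No sample size or treatment test depends on them.

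**What to change.** In Protocol section 10.1 and in the SAP:

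1. Estimate intra-individual variation from the run-in minus wash-out differences after subtracting each order's own mean, with the residuals pooled over both orders. This keeps all 15 participants and removes any mean after-effect. State the formula for the bound.
2. Report the mean difference by order, and the difference between orders, with 95% confidence intervals, as a descriptive look at persistence.
3. State that with 7 against 8 participants the expected half-width is about 0.9 to 1.4 LBGI (correlation 0.8 to 0.5), so a null result does not show that the 7-day wash-out was sufficient.

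The cost is wording and one degree of freedom (13 instead of 14). No new data or visits are needed. Using the placebo-first participants alone would also avoid the problem, but less precisely: the 95% interval for the SD would run from 0.66 to 2.04 times the estimate with 8 people, or 0.64 to 2.20 with 7. One limit remains: if the after-effect differs between people, its spread stays in the residuals of the Creon-first order.
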